STUDY PROTOCOL AND STATISTICAL ANALYSIS PLAN

Official title: Furoscix in Heart Failure Patients with Diuretic Resistance

NCT number: NCT05528588

IRB Approved date: 07-22-24

Form A

IRB #

STU-2022-0768

PROTOCOL FORM / RESEARCH DESCRIPTION

If an item does not apply to your research project, indicate that the question is "**not applicable**" – do not leave sections blank

Click once on the highlighted entry in each box to provide your response. Click the item number/letter or word, if hyperlinked, for detailed instructions for that question. If your response requires inserting a table, picture, etc, you may need to first delete the box that surrounds the answer and then insert your table or other special document.

1. Purpose and objectives. *List the purpose and objectives:*

The purpose of this study is to assess the diuretic efficiency of subcutaneous furosemide (Furoscix) compared to oral diuretic therapy for patients post heart failure (HF) hospitalization and evaluate the impact of diuretic resistance as identified by the BAN-ADHF (Blood urea nitrogen, creatinine, Natriuretic Peptide levels, Atrial fibrillation, Diastolic blood pressure, Hypertension and Home diuretic dose, and Heart Failure hospitalization) risk score.

Key Outcomes:

1. Post-treatment urine output over 8 hours. This will be assessed in mL per mg of treatment (Furoscix vs. oral diuretic).
2. Post-treatment urine sodium. Urine sodium will be assessed hourly over 8 hours post-treatment.

Safety Outcome Measures:

1. Number of participants with post-intervention need for emergency department visit or hospitalization. The count of participants with post-intervention need for emergency department visit or hospitalization for worsening heart failure is assessed.

Goals: Successful completion of this project will establish proof of concept that Furoscix provides more effective post-hospitalization diuresis than the traditional oral dose in a diuretic resistance patient population. This study will provide pilot data to guide the design of larger studies involving a diuretic-resistant heart failure population.

2. Background.

- Describe past experimental and/or clinical findings leading to the formulation of your study.
- For research involving investigational drugs, describe the previously conducted animal and human studies.
- For research that involves FDA approved drugs or devices, describe the FDA approved uses of this drug/device in relation to your protocol.

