Intervention, Setting, and Design: We are recruiting patients from UTSW and Parkland. All of the research procedures in this study will take place at the Clinical Research Unit in the Aston Building at UT Southwestern Medical Center. This will be a randomized, open-label pilot study of 70 patients with and without diuretic resistance who were recently admitted and discharged for acute decompensated heart failure with an oral diuretic regimen testing whether Furoscix is more effective at achieving post-discharge outpatient diuresis than oral diuretics. Diuretic resistance will be identified using the BAN-ADHF (Blood urea nitrogen, creatinine, Natriuretic Peptide levels, Atrial fibrillation, Diastolic blood pressure, Hypertension and Home diuretic dose, and Heart Failure hospitalization) score which has been integrated into the electronic health record. The score is integer-based with a score of ≥ 12 indicating diuretic resistance with high likelihood of poor outcomes.

Screening:

- We are requesting a partial HIPAA waiver to review electronic health records and confirm their eligibility in the study. Pre-screening will occur through the electronic health record to evaluate for inclusion and exclusion criteria and to assess if women of child-bearing potential have a pregnancy test to confirm they are not pregnant. Lab testing will be reviewed. These include review of urine drug screen, alcohol screen (if clinically indicated), NT-proBNP, creatinine clearance.
- BAN-ADHF score will be calculated.

Form A

IRB #

STU-2022-0768

- After patients are screened, patients will be approached for potential participation. If patients are interested, they will be scheduled for an in-person randomization visit optimally within 1-7 days of hospital discharge, although patients will be eligible up to 14 days after discharge.
- At the research appointment, patients will be asked if they are interested in voluntarily participating in this study.

Research Visit:

Pre-Randomization:

- Confirm eligibility
- Obtain informed consent
- Physical exam including vital signs assessment.
- Prior and concomitant medication assessment.

Randomization:

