If patients still meet all eligibility criteria and sign informed consent, they will undergo stratified randomization based on BAN-ADHF score (≥ 12 vs. < 12). Within each stratum, patients will be randomized in a 1:1 ratio (intervention: control) during the research visit. Patients will be informed via telephone prior to visit to not take home oral dose of diuretic on the day of the visit and will be instructed to hold any caffeine products such as coffee or any other drugs that could increase urine output on the day of the visit.

- **Intervention: Furoscix** – administration of subcutaneous furosemide (Furoscix) during study visit. It will be administered using the Furoscix Infusor. Per information from the Sponsor, "The Infusor is placed on the patient's abdomen for subcutaneous infusion. Furoscix is delivered subcutaneously through a small, 27-gauge, 6 mm needle. The Infusor is preprogramed to deliver 80 mg (10 mL) furosemide over 5 hours using a biphasic delivery profile of 30 mg furosemide (3.75 mL) over the first hour and 12.5 mg furosemide (1.56 mL) per hour over the subsequent 4 hours."
- **Control: Oral Diuretic** - administration of oral diuretic during study visit. Patients will bring their home prescription of oral diuretic and will take the oral formulation while in the visit. If the patient did not bring their home dose, an equivalent oral dose will be provided from the UT Southwestern Investigational Drug Service.

The intervention arm (Furoscix over 5 hours at 8 mg/mL) will be compared to a usual care group (home oral diuretic dose prescribed by discharge physician). Patients will be monitored for 8 hours in the Clinical Research Unit post-drug administration for clinical safety and to measure clinical response.

Other research procedures:

- Patients will be instructed to void immediately before dosing (pre-dose urine) and this sample will be discarded. After medication administration, urine from spontaneous voids during post-dose phases will be collected and recorded. Urine sodium measurements will be obtained at hourly intervals. Urine from each collection period must be refrigerated until the end of the collection period. Total volume of urine produced will be assessed over 8 hours post-study drug administration. 5 mL of each hourly urine sample will be sent for a urine sodium lab test in a yellow round bottom tube.

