- Collect approximately 10 mL of blood for a blood test to check patient's electrolytes. This will be done at the end of the research visit.
- Call participants in 7 days after their research visit to assess if patient has had a presentation to urgent care, emergency department, or is re-hospitalized for acute exacerbation in heart failure.

Compensation:

To account for a full day of research monitoring, patients will be compensated \$250 for their participation in the study with the UTSW ClinCard.

Data Safety and Monitoring:

Patient safety will be tracked over the study. For any adverse events (AE) that occur during their participation in the study, medical care will be provided and patients will be followed until resolution. See Form D for more details.

Form A

IRB #

STU-2022-0768

Privacy and Confidentiality:

To protect patient's privacy and confidentiality, we will ensure the consent process takes place in a private area and conduct research in secure areas where others will not have access to their PHI. All PHI collected during the study will be coded with a Subject ID using a randomized code. The key to the code will be kept on a password database in the research coordinator's locked office. Only authorized personnel listed on Form B will have access to the data. Any hard copy documents such as the signed consent form will be kept in the research coordinator's locked office.

Statistical Analysis:

This study will assess the primary outcomes of greater diuretic efficiency as measured by total urine output and urine sodium. As the Furoscix group will receive 80 mg of subcutaneous furosemide and the control group will take a home dose of oral diuretic, urine output will be normalized per mg of treatment administered. Differences in total urine produced will be compared between Furoscix versus oral diuretic groups. The urine sodium will be assessed hourly, and will be compared across the two groups.

As this study is a preliminary pilot study to assess the effect of Furoscix on diuretic efficacy, we have chosen a convenience sample of 70 patients to allow for a comparison between patients who receive Furoscix and those who do not receive Furoscix. The results of this trial will serve as a precursor for a larger, multicenter trial of Furoscix in patients with diuretic resistance.

4.b. List of the study intervention(s) being tested or evaluated under this protocol

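### The pre-dose void is discarded untested, so urine sodium, a primary outcome, has no time-0 value: a cheap chance to gain precision is missed, but the comparison is not biased

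*Combined protocol and SAP*

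**What the plan says.** Section 4.a, under Other research procedures, sets out the urine handling. Before dosing: "Patients will be instructed to void immediately before dosing (pre-dose urine) and this sample will be discarded". After dosing: "After medication administration, urine from spontaneous voids during post-dose phases will be collected and recorded". The sodium assay is tied to the post-dose collections only: "5 mL of each hourly urine sample will be sent for a urine sodium lab test in a yellow round bottom tube".

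Urine sodium is not a minor measure here. Section 1 (Key Outcomes) lists it: "Urine sodium will be assessed hourly over 8 hours post-treatment". The Statistical Analysis part of section 4.a counts it among the "primary outcomes of greater diuretic efficiency as measured by total urine output and urine sodium". The analysis is given in one sentence: "The urine sodium will be assessed hourly, and will be compared across the two groups". No model, covariate or change score is named.

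No other part of the plan supplies a pre-dose urine sodium. The chart review at screening covers other tests: "These include review of urine drug screen, alcohol screen (if clinically indicated), NT-proBNP, creatinine clearance". The pre-randomization list has eligibility, consent, examination and medication review, but no urine test. The one study sample that is not urine is a blood draw for electrolytes, of which the plan says: "This will be done at the end of the research visit".

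**The concern.** Every patient already produces a urine sample just before the study dose, on a day when the home diuretic and caffeine are withheld. Emptying the bladder is needed so that earlier urine is not counted in the 8-hour volume. That purpose is met by leaving the void out of the volume, and it does not require discarding the urine without an assay.

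Three things are lost, and none can be recovered once the sample is gone:

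- **Precision.** Patients differ in urine sodium before any study drug, and part of that variation may carry into the post-dose values. With about 35 per arm, a prognostic covariate could be worth having.
- **Description of response.** Without a time-0 value the report cannot show where each patient started.
- **Pilot information.** Section 1 says the study should inform the design of larger ones. The correlation between pre-dose and post-dose sodium is needed to size a baseline-adjusted trial, and this pilot could estimate it at almost no cost.

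**Working it through.** **Inputs from the documents.** Total N = 70, a convenience sample; 1:1 allocation within BAN-ADHF strata, so about 35 per arm (section 4.a). The plan gives no alpha, power, effect size or SD, so it has no design figure to reproduce.

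**Assumptions.** r is the within-arm correlation between pre-dose and post-dose urine sodium, beyond what the stratum explains. The documents do not give it, so a range from 0.1 to 0.7 is shown. For scale only: two-sided alpha 0.05, 80% power, normal approximation.

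**Formulas.**

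1. Variance of the adjusted arm difference relative to the unadjusted one: 1 − r².
2. Unadjusted sample size with the same precision: 70 / (1 − r²).
3. Detectable difference in SD units: (1.960 + 0.842) × √(2/35) × √(1 − r²). With r = 0 this is 2.802 × 0.239 = 0.67.
4. Power for a true difference of 0.5 SD: Φ(0.5 / [√(2/35) × √(1 − r²)] − 1.960). With r = 0 this is Φ(2.092 − 1.960) = 55%.

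| Assumed r | Variance cut | Equivalent unadjusted N | Detectable difference (SD) | Power at 0.5 SD |
|---|---|---|---|---|
| 0 (no time-0 value) | 0% | 70 | 0.67 | 55% |
| 0.1 | 1% | 70/0.99 = 71 | 0.67 | 56% |
| 0.2 | 4% | 70/0.96 = 73 | 0.66 | 57% |
| 0.3 | 9% | 70/0.91 = 77 | 0.64 | 59% |
| 0.5 | 25% | 70/0.75 = 93 | 0.58 | 68% |
| 0.7 | 51% | 70/0.51 = 137 | 0.48 | 83% |

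The table ignores the small cost of estimating the covariate's slope. For a normally distributed covariate with 35 per arm, that cost multiplies the variance by about 1 + 1/(2 × 34 − 2) = 1 + 1/66 = 1.015. At r = 0.1 it cancels the gain (0.99 × 1.015 = 1.005). From r = 0.3 upwards it changes little.

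**Chance imbalance is the same loss.** The SD of the chance difference in baseline means is √(2/35) = 0.24 SD. At r = 0.5 it moves the unadjusted result by 0.5 × 0.24 = 0.12 SD. Squared, that is 0.25 × 2/35 = 0.0143, which is exactly the 25% of variance in the table. It must not be counted as a second harm.

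**The case against.** The strongest reply is that nothing planned is broken. The outcome is defined as a post-treatment level and compared between randomized arms. No change score or baseline-adjusted analysis is promised, how far each treatment raises sodium is not a stated objective, and a pilot with a convenience sample misses no precision target. All of that stands. This is a missed measurement, and the plan does not contradict itself.

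A reader might infer that the arm comparison is confounded by differences in diet, renal sodium handling or time since discharge. The documents do not support that. Under 1:1 randomization such differences are chance variation, and the standard error of an ordinary unadjusted comparison already reflects them. The stratifying score also includes blood urea nitrogen, creatinine and home diuretic dose, so some of the renal and diuretic differences are partly balanced by design.

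Two further points stand in part. First, nothing in the documents supports a moderate or high r. The pre-dose void is a spot sample built up over an uncontrolled period, while the later samples are hourly and driven by the drug. The low values in the table are therefore as admissible as the high ones. Second, the plan does not say whether the sodium outcome is a concentration or an excreted amount. If it is an amount, a spot concentration is not its baseline. It can still serve as a covariate, because it is fixed before dosing.

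None of this removes the case for one inexpensive assay on urine that every patient already passes.

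**Conclusion.** The point holds as a cheap improvement. The plan discards the only pre-dose urine untested and has no other source of a pre-dose urine sodium for a primary outcome. The planned comparison remains valid and unbiased in expectation. The loss is precision, a description of within-patient response, and an estimate of r for the larger trial.

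The facts are certain from the text, but the size of the benefit is not. It runs from practically nothing at r = 0.1, through a 25% variance reduction at r = 0.5, to about half the variance at r = 0.7. All of these r values are assumptions. Quoting the upper end alone as the expected gain would go beyond the documents.

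**What to change.** 1. **Sampling.** Reword the instruction so that the pre-dose void stays out of the 8-hour volume but 5 mL of it is sent for urine sodium as the time-0 sample, in the same tube and with the same handling as the hourly samples.
2. **Analysis.** Include the time-0 sodium and the BAN-ADHF stratum as covariates in the between-arm comparison of post-dose urine sodium. State whether the outcome is a concentration or an excreted amount. If it is an amount, use the spot concentration only as a prognostic covariate and do not compute a change score.
3. **Missing time-0 values.** Keep these patients in the analysis, including any treated before the change. Impute the single overall mean of the time-0 value and add a missing indicator. A complete-case adjusted analysis would drop them and could lose more precision than the covariate gains.
4. **Reporting.** Report the observed r for use in planning the larger trial.

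**Cost.** At most 70 extra assays, against up to 8 × 70 = 560 already planned, plus short additions to the protocol and analysis text. There is no new patient procedure. The downside is that the gain may be small if r is low, and patients already treated cannot supply the value.

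### Does counting the 8-hour urine window from after drug administration give the 5-hour infusion arm a different window from the oral arm?

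*Combined protocol and SAP*

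**What the plan says.** Both key outcomes in section 1 cover 8 hours and are described as post-treatment: urine output in mL per mg, and urine sodium measured hourly.

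Section 4.a (Randomization) describes the two treatments. The infusor is set to "deliver 80 mg (10 mL) furosemide over 5 hours using a biphasic delivery profile of 30 mg furosemide (3.75 mL) over the first hour", with the rest given over the next 4 hours. Controls take their home oral diuretic at the visit. The comparison is put this way: "The intervention arm (Furoscix over 5 hours at 8 mg/mL) will be compared to a usual care group". On follow-up at the visit it says: "Patients will be monitored for 8 hours in the Clinical Research Unit post-drug administration for clinical safety and to measure clinical response".

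Section 4.a (Other research procedures) gives the urine collection in this order:

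- The baseline step comes first: "Patients will be instructed to void immediately before dosing (pre-dose urine) and this sample will be discarded".
- The collection itself is the next step, and its start is worded as follows: "After medication administration, urine from spontaneous voids during post-dose phases will be collected and recorded".
- The length of the window is given a little further on: "Total volume of urine produced will be assessed over 8 hours post-study drug administration".

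Section 5.a repeats the 8 hours of monitoring after medication. Section 4.a (Compensation) calls the visit a full day, without a number of hours. No sentence says whether the time after administration is counted from its start or its end.

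**The concern.** For a tablet, the start and end of administration coincide. For the infusor they are 5 hours apart. Every timing statement uses a word such as post or after, so a literal reader could start the Furoscix clock when the infusion stops. Two consequences would be possible:

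- Collection begins only at that point. The urine made while the drug is running is then missed.
- Collection begins with dosing but continues until 8 hours after the infusion ends. The Furoscix total then covers more hours than the oral total.

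Either would distort total volume, and they would probably do so in opposite directions. The hourly sodium series would be out of step between arms if the clock were shifted. Volume and sodium are the two key outcomes of a pilot meant to guide a larger trial, so the question is worth settling.

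A second worry concerns a clock that starts with dosing. The later milligrams of the infusion have less time to act before hour 8, yet output is divided by the full 80 mg.

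**Working it through.** **Inputs.** From section 4.a (Randomization): 30 mg (3.75 mL) in hour 1, then 12.5 mg (1.56 mL) per hour for 4 hours. From section 1 and section 4.a: an 8-hour window. Assumption: oral dosing takes about 0 hours, since no duration is stated.

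**The plan's own infusion figures.**

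- Dose: 30 + 4 × 12.5 = 80 mg, as stated.
- Volume: 3.75 + 4 × 1.56 = 9.99 mL, which is the stated 10 mL after rounding.
- Duration: 1 + 4 = 5 hours, as stated.

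**Three readings, on a clock that starts when dosing starts.**

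| Reading | Furoscix | Oral | Result |
|---|---|---|---|
| A. Clock from start of dosing | 0–8 h | 0–8 h | Equal windows; 5 infusion hours plus 8 − 5 = 3 hours after |
| B. Clock and collection from end of administration | 5–13 h | 0–8 h | Overlap 8 − 5 = 3 hours; infusion urine lost |
| C. Collect from start, stop 8 h after end | 0–13 h | 0–8 h | 13/8 = 1.625 times as long |

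For scale under C, assume equal flow in both arms of 100 to 300 mL/h (not in the documents). The 5 extra hours add 5 × 100 = 500 mL to 5 × 300 = 1,500 mL. Divided by 80 mg, that is 6.25 to 18.75 mL/mg in favour of Furoscix. Under B the error would probably run against Furoscix, but the documents give no hourly urine profile from which to size it.

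**Which reading does the text support?**

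- *The discarded void.* Emptying the bladder just ahead of the dose makes the next urine attributable to the period after the dose began. Under B, collection would start 5 hours later and the void would serve no purpose in the Furoscix arm. It fits A.
- *The outcome length.* Section 1 and section 4.a both fix volume at 8 hours. A 13-hour total contradicts this, so C is excluded by the text.
- *The visit.* B and C need at least 5 + 8 = 13 hours on site, on top of consent, examination and randomization. The plan describes 8 hours of monitoring within one full day. This is suggestive, not conclusive.

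**Time to act under A.** The mean time from delivery to hour 8, weighted by dose, is

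(30 × 7.5 + 12.5 × (6.5 + 5.5 + 4.5 + 3.5)) / 80 = (225 + 250) / 80 = 475 / 80 = 5.94 h,

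against 8 h for a dose swallowed at time zero: 1 − 5.94/8 = 26% less. The arithmetic is right, but it measures hours since delivery, not urine. It allows nothing for absorption of the oral dose, and the documents give no onset or duration data for either product. It is therefore not an estimate of bias in mL/mg. Nor would defining time zero remove it, because it follows from comparing a 5-hour infusion with an oral dose over any common 8-hour window.

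**The case for a change.** The best argument for a change is that the window of a key outcome should not rest on inference. The pre-dose void is one pointer, set beside several sentences that say post or after administration. If staff did follow the end of the infusion, the volume comparison would be badly off, and one sentence would prevent that at no cost in patients, tests or visit time.

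Part of this stands. Time zero is undefined in the text, and the full-day description does not settle it. The study schema in section 3 is a figure whose content could not be checked, so it may or may not show the timing.

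The rest does not carry the point. No sentence starts the clock at the end of the infusion, so a mismatch is a possibility under one reading and not a feature of the design. All procedures take place in one Clinical Research Unit, which makes divergent readings by different staff less likely. The 5/8 = 63% that can be attached to reading B is a share of hours, not of urine. For sodium, the plan specifies hourly measurements and defines no cumulative excretion. A shifted clock would misalign that series, but there is no cumulative sodium total to distort.

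**Conclusion.** The concern does not call for a change. The gap is real but small: the plan leaves unsaid that the 8 hours run from the start of dosing. The order of procedures, the discarded void and the fixed 8-hour outcome all point that way, and a unit following them would collect 0 to 8 hours in both arms. The difference in window length is then 0 hours, and no infusion urine is lost.

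This rests on two assumptions: that oral dosing takes effectively no time, and that staff start collection after the pre-dose void, as the sequence implies. The 5-to-13-hour window arises only if they do not, and the 13-hour total would also contradict the stated outcome.

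The 3 hours of collection after the infusion ends, and the 5.94 versus 8 hours per mg, are matters for interpreting mL/mg. They come with the choice to compare an infusion with an oral dose over a fixed visit, and clarifying the clock would change no result.
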